1. INTRODUCTION/ REVIEW

Enlarged prostate represents the most common cause of lower urinary tract symptoms (LUTS) in elderly men including irritative, obstructive urinary symptoms or even urinary retention that significantly affects the quality life (QoL). (1)

Transurethral resection of the prostate (TURP) represents the standard surgical technique for the management of benign prostatic hyperplasia (BPH) with a prostate size less than 80 ml. However, considerable morbidities are associated with larger sizes. (1,2)

Endoscopic enucleation of the prostate (EEP) has been recognized as a treatment option for large prostatic adenomas, since first described by Hiraoka et.al, in 1986 (3), it started to gain popularity despite the long learning curve. Many studies have evaluated its efficacy against the gold standard open prostatectomy in large prostate size more than 80ml and showed its safety and efficacy. (2)

EEP represents an anatomical surgical technique resembling a surgeon's finger in open prostatectomy where any energy source that provides adequate haemostasis could be used (4). Many studies concluded that EEP relies on the surgeon's skills rather than the energy source itself (5,6). Holmium laser enucleation of the prostate (HoLEP) was first described by Gilling in 1998 (7) and was proven to be effective with no prostate size limitation with adequate haemostasis (8), recently it has been approved as a standard treatment for large prostatic adenoma (2), bipolar enucleation of the prostate (BPEP) has been introduced as an alternative energy source with a promising outcome with equal safety and efficacy (4,9,10).

Few studies evaluated both techniques, one study was done by Shoma et al. showing no statistical difference regarding safety and efficacy between both techniques(11), another study conducted by Enikeev et al. reported earlier recovery and catheter removal with HoLEP compared to BPEP (9). However, cost-effectiveness was never been evaluated before between both techniques especially in developing countries.

With such scarce information, we aimed through our study to compare these two energy sources in the enucleation procedure of the prostate in terms of safety, efficacy, and cost-effectiveness in the management of BPH in large prostatic adenoma more than 80 ml.

2. AIM/ OBJECTIVES

To compare the clinical outcome in the form of safety, efficacy and cost effectiveness between Holmium laser enucleation of the prostate versus bipolar transurethral enucleation of the prostate

3. METHODOLOGY:

Patients and Methods/ Subjects and Methods/ Material and Methods

Type of Study: prospective randomized clinical trial

Study Setting: Operation ward - Ain Shams University hospitals.

Study Period: 4/2018 till we finish the follow up period

Study Population: Egyptian male patients attending Ain Shams University hospitals Urology clinic

Sample size: It was dose using STATA program, setting alpha error at 0.05 and power at 90% based on results from previous study (Enikeev et.al,2018) that showed a mean catheter removal time in HoLEP group was 1.3 -/+0.6 while in Transurethral electrocautery enucleation group was 3.8 -/+1.7 (9), based on that, the needed sample is 50 cases per group taking in account 20% drop out rate.

Group A: 50 Patients will undergo prostatic resection using HoLEP

Group B: 50 Patients will undergo BPEP

Procedures: each procedure will be done by 2 expert surgeons who performed over 50 cases of enucleation with each energy source. In group 1, the HoLEP procedure will be done under either

general or spinal anesthesia, using a Holmium laser device (cyber Ho 100-watt, Quanta device, Milano, Italy) with a 50-watt power, 2.5 joules and 25 MHz frequency. A 550 nm flexible laser fiber. In group 2, the BPEP procedure will be done by a Karl Storz device, using a bipolar resection loop or button loop according to the availability and surgeon's preference, tissue morcellator with reusable blades (Ricjard Wolf Inc.) will be used to morcellate the prostatic adenoma.

The enucleation technique is nearly similar in both groups regardless of the energy source used, a 26 Fr continuous flow resectoscope (Karl Storz, Germany) with saline irrigation. The procedure will start by incision along the deepest prostatic groove using a bilobed technique where each lobe will be enucleated separately or a trilobed technique to separate a huge median lobe first then to continue as bilobed technique, the incision continues till verumontanum, then we will perform a circumferential marking proximal to the external urethral sphincter for demarcation, lateral incision will be done till the prostatic capsule and start enucleation using a mechanical force of the resectoscope with assisted energy source either Holmium laser or bipolar electrocautery, and then we will proceed anterolateral around the prostatic adenoma, aiming for early apical separation to avoid traction of the external sphincter with mucosal strip to be left intact more proximal to avoid dissemination of energy to the sphincter, anterior commissurotomy to be done to separate each lobe separately the procedure mimic figure enucleation in open surgery by using the resectoscope assisted energy source and then to proceed anteriorly till the bladder neck and then we complete the enucleation from anterior to lateral and move downward to finally separate the adenoma from posteriorly into the bladder, in this way we avoided the sub-trigonal injury or ureteric injury, then we perform the other lobe in the same way, after separation of each lobe we check the ureteric orifices and adequate hemostasis was done, finally morcellator will be used to cut down prostatic adenoma into small chips to be removed.

Inclusion criteria: Men who are fit for surgery and need a surgical resection of the prostate larger than 80 ml including:

1. Bothersome LUTS with an IPSS score over 19
2. Refractory hematuria
3. Upper urinary tract affection
4. Recurrent UTI secondary to prostatic enlargement
5. Maximum uroflow rate (Qmax) below 10 ml/sec.

6. bladder diverticula
7. Urinary retention whether recurrent acute attacks with failure of medical treatment or chronic retention.

Exclusion criteria: Patients with:

1. Neurogenic bladder
2. Previous prostate or urethral surgery
3. Associated urethral stricture
4. Prostate cancer diagnosed by TRUS biopsy
5. Bladder stones,

Ethical Considerations: Approval will be obtained from the ethical committee at Ain shams University before starting the research.

Study Procedures: The patients will undergo the following:

Preoperative:

1) History:

Including medical history, surgical history, drug history, International Prostate Symptom Score (IPSS) and quality of life score (QoL).

2) Clinical Examination:

Including abdominal, pelvic and digital rectal examination (DRE).

3) Laboratory investigations:

As Haemoglobin level, serum creatinine, urea, sodium, potassium and prostate specific antigen (PSA).

4) Radiological investigations:

As pelvi-abdominal ultrasound to assess prostate volume and postvoiding residual urinary volume (PVR).

5) Maximum Flow Rate (Qmax).

Intraoperative: Vital data monitoring, operative time and the need for blood transfusion

Postoperative Follow-up Protocol:

Patients will be evaluated immediately postoperative with vital signs (Blood pressure, Heart rate), abdominal examination, degree of haematuria, haemoglobin level drop and Sodium level changes.

Patients will be re-evaluated at 6 and 12 months postoperatively with the IPSS, QoL, Pelvic U/S (to assess prostate volume and post voiding residual urinary volume (PVR)) ,

Maximum Flow Rate (Qmax) and Total PSA .

Data collection and outcome measures:

Primary outcomes:

1. Catheter removal time

Secondary Outcomes:

1. Operative time, enucleation time
2. Intraoperative need of blood transfusion and hemoglobin drop
3. Conversion to other type of surgeries
4. Post-operative drop in hemoglobin level
5. Duration of hospital stay
6. Postoperative complication: urinary tract infection, stress incontinence, hematuria, urine retention
7. Post voiding residual urine, Qmax, PSA, Prostate volume, QoL and IPSS 1 and 12 months postoperative
8. Delayed complication up to 12 months postoperative including urethral stricture, urinary retention, incontinence or bladder neck contracture.
9. Cost effectiveness of each procedure.

Statistical Analysis: The data will be collected, processed and statistically analyzed. Description of the quantitative variable will be done as mean and standard deviation and student t-test will be used to compare the two groups in parametric data while the qualitative data will be shown as frequency and compared using Chi square test. The results will be considered significant with P-value less 0.05 and high significant if less than 0.01, results with P-value ≥ 0.05 will be considered non-significant. Analysis of the data will be done using IBM SPSS software (Statistical program for social science version 21).

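### Retention at entry is plausibly prognostic for catheter removal time and PVR, but no stratification is described and the planned t-test does not adjust for it, so precision may be lost

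*Combined protocol and SAP*

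**What the plan says.** The inclusion criteria (Methodology) list several alternative reasons for surgery on a prostate above 80 ml. They include an IPSS above 19, a Qmax below 10 ml/sec, haematuria, recurrent infection and, as item 7, "Urinary retention whether recurrent acute attacks with failure of medical treatment or chronic retention". The only exclusion that concerns bladder function directly is neurogenic bladder.

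The single primary outcome is "Catheter removal time". PVR is among the secondary outcomes. The documents state no criterion for removing the catheter.

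The Type of Study line calls the trial prospective and randomised. It describes no sequence, blocking, stratification or concealment. Under Statistical Analysis, "student t-test will be used to compare the two groups in parametric data", with a chi-square test for qualitative data. No covariate, baseline adjustment or analysis by entry indication is mentioned.

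The Sample size paragraph works from "mean catheter removal time in HoLEP group was 1.3 -/+0.6" and "Transurethral electrocautery enucleation group was 3.8 -/+1.7", and concludes that "the needed sample is 50 cases per group taking in account 20% drop out rate". No time unit is given for these figures.

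**The concern.** A bladder that has been in retention may empty less well after the obstruction is removed, whichever energy source was used. If so, retention at entry would explain part of the spread in catheter removal time and PVR. It is known from the history before surgery, yet the plan as written makes no use of it.

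What is at stake is precision. An unadjusted test leaves the between-patient variation due to retention in the error term, and with 40 to 50 men per arm the share in retention can differ between arms by chance. Both widen the confidence interval for the device difference. There is also a reporting cost. Postoperative retention is counted as a complication, and readers cannot put that count in context unless retention at entry is shown by arm.

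**Working it through.** **Inputs from the Sample size paragraph.** "setting alpha error at 0.05 and power at 90" per cent; means 1.3 and 3.8, so a planned difference of 2.5; SDs 0.6 and 1.7; 50 per arm with 20% dropout, so 50 × 0.8 = 40 evaluable. A two-sided test is assumed, as sidedness is not stated.

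**Assumptions, not in the documents.** The share in retention at entry is p = 20-40%. Their extra catheter time is e = 1-2 time units. The smaller true difference is 1.0. The planning SD is taken as the variation that remains once retention is accounted for.

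**Step 1, the plan's own figure.** The average variance is (0.6² + 1.7²)/2 = (0.36 + 2.89)/2 = 1.625, so SD = 1.275. By the normal approximation, n per arm = 2(1.96 + 1.282)² × SD²/2.5².
- SD 1.275: 5.5, so 6 per arm, or 8 after 20% dropout.
- SD 1.7: 9.7, so 10 per arm, or 13 after dropout.

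The stated 50 per arm is not reproduced. That is a separate matter and does not support this point; the surplus in fact cushions the precision loss.

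**Step 2, added variance.** Retention adds e² × p(1 − p), and total SD = √(1.625 + e² p(1 − p)).

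| p | e | added variance | total SD |
|---|---|---|---|
| 0.2 | 1 | 0.16 | 1.34 |
| 0.3 | 1 | 0.21 | 1.35 |
| 0.4 | 1 | 0.24 | 1.37 |
| 0.2 | 2 | 0.64 | 1.50 |
| 0.3 | 2 | 0.84 | 1.57 |
| 0.4 | 2 | 0.96 | 1.61 |

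The unadjusted confidence interval is therefore wider by a factor of 1.34/1.275 = 1.05 to 1.61/1.275 = 1.26.

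**Step 3, chance imbalance.** The SD of the between-arm difference in share is √(2p(1 − p)/n). For p = 0.3 and n = 50 it is 0.092, so the 95% range is ±1.96 × 0.092 = ±0.18. Multiplied by e, this moves the observed difference by up to ±0.18 (e = 1) or ±0.36 (e = 2), which is 7% to 14% of 2.5. With n = 40 the figures are ±0.20 and ±0.40. This is not an extra error on top of step 2: it is the same variation, already contained in the t-test's standard error.

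**Step 4, bias and type I error.** In 40,000 simulated trials per setting (p = 0.3 with e = 2, and p = 0.5 with e = 3; 40 and 50 per arm), the unadjusted t-test rejected a true null 4.9-5.0% of the time. A true difference of 1.0 was estimated as 1.00 on average.

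**Step 5, power.** Power = Φ(difference/(SD × √(2/n)) − 1.96).
- True difference 2.5, n = 40: above 99.9% throughout.
- True difference 1.0, n = 40, p = 0.2, e = 1: 1/(1.336 × 0.2236) − 1.96 = 1.39, power 92%.
- True difference 1.0, n = 40, p = 0.4, e = 2: 1/(1.608 × 0.2236) − 1.96 = 0.82, power 79%.
- True difference 1.0, n = 40, retention variance fully removed: 1/(1.275 × 0.2236) − 1.96 = 1.55, power 94%.
- With all 50 per arm analysed (√(2/50) = 0.2), the same formula gives 87-96% unadjusted against 97.5% adjusted.

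**The case against.** The trial team could fairly say that enrolling across the usual indications for surgery is a legitimate pragmatic choice, that randomisation balances retention in expectation, and that the t-test already allows for chance imbalance. All of that stands. A reader might infer that catheter time and PVR will reflect bladder condition rather than the energy source, or that the result cannot be attributed to the device. The documents do not support that: retention precedes randomisation, so it adds noise rather than confounding, as step 4 shows.

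The team could add that nothing in the protocol says how many men are in retention or how long they keep a catheter. With no stated removal criterion, the link to bladder emptying is clinical plausibility only. That also stands. The 2-unit scenario is hard to square with the HoLEP planning SD of 0.6, because its added variance of 0.64-0.96 exceeds that arm's whole variance of 0.36, unless the cited study had few such men. At e = 1 alone, unadjusted power for a difference of 1.0 is 91-92%, and the gain from adjustment is small.

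Two further inferences should be resisted. One is that preoperative PVR and Qmax are unusable in men in retention. The protocol lists both measurements without exception and does not say that these men are catheterised at entry; men with recurrent attacks may void between them. The other is that men with "bladder diverticula" need a separate sensitivity analysis. The documents supply no figure from which to size such an effect.

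The objection does not settle the matter where it relies on the 2.5 difference. The reference list describes the source of that figure as a retrospective comparison of monopolar with laser enucleation, whereas this trial tests bipolar. The Introduction also cites a comparison of the two trial techniques that found no statistical difference in safety or efficacy. A true difference well below 2.5 is therefore plausible on the protocol's own text.

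**Conclusion.** The point holds as one of precision and clear reporting. Retention at entry is pooled with other indications, no stratification is described, and the stated analysis is unadjusted. The planned test remains valid and unbiased.

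The consequence is minor if the true difference is 2.5. If it is about 1.0, not adjusting lowers power from about 94% to somewhere between 79% and 92% with 40 evaluable men per arm. The lower end depends on the 2-unit assumption, which fits the planning figures poorly. All of these sizes rest on the assumed share in retention, the assumed extra catheter time and the choice of 1.0. No size can be given for PVR, because the documents contain no PVR planning figures.

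The undescribed allocation method and the undefined removal criterion are separate gaps. Unlike this one, they could lead to real bias.

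**What to change.** - **Catheter removal time:** replace the unadjusted t-test with a linear model containing treatment arm and retention at entry (yes/no), pre-specified as the primary analysis.
- **PVR:** adjust for retention at entry and for baseline PVR where available, stating in advance how a missing baseline value is handled.
- **Allocation:** if it is still open, stratify by retention at entry. If it has closed, the covariate alone suffices.
- **Reporting:** show the number in retention at entry by arm, and tabulate catheter removal time by retention status within each arm.

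The cost is one binary variable taken from the history, one model term and one descriptive table. Eligibility, patient numbers, visits and tests are unchanged. Fixing the term before the data are seen also avoids a post hoc choice should the arms turn out unbalanced.

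### With a t-test as the only method and no missing-data rule, the 12-month secondary comparisons would by default omit men lost to follow-up and ignore their earlier values

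*Combined protocol and SAP*

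**What the plan says.** - **Expected loss.** Under Methodology, Sample size: "the needed sample is 50 cases per group taking in account 20% drop out rate". The sentence concerns catheter removal time and names no visit at which the 20% applies.
- **Repeated measurement.** IPSS, QoL, PSA, prostate volume, residual urine and Qmax are all listed preoperatively. The Postoperative Follow-up Protocol then states "Patients will be re-evaluated at 6 and 12 months postoperatively with the IPSS, QoL", with the other four outcomes measured at the same visits. Secondary outcome 7 gives a different first visit: "Post voiding residual urine, Qmax, PSA, Prostate volume, QoL and IPSS 1 and 12 months postoperative".
- **Analysis.** Under Statistical Analysis, the only method for quantitative outcomes is that "student t-test will be used to compare the two groups in parametric data". Qualitative outcomes get a chi-square test. The section gives no analysis population, missing-data rule, repeated-measures model, baseline adjustment or sensitivity analysis.

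**The concern.** A two-sample t-test at 12 months needs a 12-month value from each man it includes. If nothing else is specified, a man who attended the first follow-up visit and then stopped contributes nothing to the 12-month comparison, although his preoperative and first postoperative values are on file. The result is unbiased for the arm difference only if loss is unrelated to outcome, or is related to it in the same way in both arms.

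Efficacy is one of the three stated aims, and outcome 7 carries it. At stake is a modest distortion of those secondary comparisons, and the freedom to decide how missing men are handled after the results are known.

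**Working it through.** **The plan's own figure.** The drop-out step is consistent: 40 / (1 − 0.20) = 50 per group. The 40 does not follow from the stated inputs, which are "setting alpha error at 0.05 and power at 90" per cent, "a mean catheter removal time in HoLEP group was 1.3 -/+0.6" and "Transurethral electrocautery enucleation group was 3.8 -/+1.7". The root-mean-square SD is √[(0.6² + 1.7²)/2] = 1.275 and the difference is 2.5. So n = 2 × (1.96 + 1.2816)² × 1.275² / 2.5² = 5.5, or 6 per group, and 6 / 0.8 = 7.5, or 8 per group. That is a separate matter and does not affect this point.

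**Assumptions, since the documents give none of these.** There are 50 men per arm and no true difference between arms. Earlier and 12-month values are normal with SD 1 and correlation ρ = 0.4, 0.6 or 0.8. The log-odds of loss by 12 months is −1.75 + slope × earlier value. This loses about 15% at slope 0 and about 20% at slope 1.2.

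**Bias of the 12-month mean in one arm.** It equals ρ × m, where m is the shift in the mean earlier value among the men retained. In simulation m is about 0.08 SD at slope 0.5 and 0.20 SD at slope 1.2.

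- Slope 0.5, one arm: 0.4 × 0.08 = 0.03 up to 0.8 × 0.08 = 0.06 SD.
- Slope 1.2, one arm: 0.4 × 0.20 = 0.08, 0.6 × 0.20 = 0.12 and 0.8 × 0.20 = 0.16 SD.
- Slope 1.2, opposite directions: double these, so 0.16, 0.24 and 0.32 SD.

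**False-positive rate.** For slope 1.2 in one arm, about 40 and 42.5 men remain, so SE = √(1/40 + 1/42.5) = 0.220. At ρ = 0.8 the shift is 0.16 / 0.220 = 0.73 SE, and P(Z > 1.96 − 0.73) + P(Z < −1.96 − 0.73) is about 11%. At ρ = 0.4 the shift is 0.36 SE, giving about 6.5%. Simulations that counted actual t-test rejections agree:

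| Loss mechanism | Bias, SD (ρ = 0.4, 0.6, 0.8) | False positives, % |
|---|---|---|
| Unrelated to outcome | 0, 0, 0 | 5 |
| Slope 0.5, one arm | 0.03, 0.05, 0.06 | 5 to 6 |
| Slope 1.2, one arm | 0.08, 0.12, 0.16 | about 7 to 11 |
| Slope 1.2, same direction in both arms | 0, 0, 0 | 5 |
| Best and worst both lost, one arm | 0, 0, 0 | 5 |
| Slope 1.2, opposite directions | 0.16, 0.24, 0.32 | 11 to 31 |

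A likelihood estimate that uses the earlier value has bias below 0.005 SD in these cases. That is expected, because loss was made to depend only on that observed value.

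**Precision.** If loss is unrelated to outcome, the variance relative to the t-test is 1 − d × ρ², where d is the proportion lost.

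- At d = 0.20 the reductions are 0.20 × 0.16 = 3%, 0.20 × 0.36 = 7% and 0.20 × 0.64 = 13%.
- At d = 0.15 they are about 2, 5 and 10%.
- With opposite-direction loss at ρ = 0.4, the model's variance is about 4% larger.

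**Scale.** With 40 men per arm, the difference detectable at 90% power is (1.96 + 1.2816) × √(2/40) = 0.72 SD. A bias of 0.16 SD is 0.16 / 0.72 = 22% of that.

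**The case against.** The best reply is that the plan is silent rather than wrong, and that the bias needs special conditions. Several parts of this stand.

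- A reader might infer that the plan prescribes an attendees-only analysis. It does not. That is the default of a t-test with no missing-data rule, and imputation is neither planned nor excluded.
- A reader might infer that the plan predicts 20% missing at 12 months. The figure sits in the sample-size sentence and is tied to no visit, so any loss rate at 12 months is an assumption.
- A reader might take the 31% error rate as the expected size. It needs strong dependence running in opposite directions in the two arms, together with a correlation of 0.8. The documents describe the two enucleation techniques as nearly the same and give no reason to expect this.
- A reader might argue that men doing very well or very badly stop attending. Symmetric loss of both extremes gives no bias in the mean. One-sided loss that differs by arm is what does harm.
- A reader might think the trial's main result is threatened. Catheter removal happens soon after surgery, so the primary comparison is hardly touched.
- The model is not a complete rescue. It assumes that observed values explain the loss, and a man lost before the first postoperative visit has only baseline values.

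The reply does not remove the gap. The plan allows for loss, schedules earlier measurements, and names a method that cannot use them.

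**Conclusion.** The point holds for the secondary outcomes IPSS, QoL, Qmax, residual urine, PSA and prostate volume at 12 months, and should be corrected. Under dependence confined to one arm, the bias is 0.03 to 0.06 SD at a slope of 0.5 and 0.08 to 0.16 SD at a slope of 1.2. The corresponding false-positive rates are 5 to 6% and about 7 to 11%, against a nominal 5%. If loss works alike in both arms there is no bias. These sizes rest on assumed correlations of 0.4 to 0.8, assumed loss of 15 to 20% by 12 months, and an assumed loss mechanism. The case for change is protection against bias and a rule fixed in advance, since the precision gain is small and sometimes absent.

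**What to change.** 1. Reconcile the first follow-up visit, which is 6 months in the Postoperative Follow-up Protocol and 1 month in secondary outcome 7. The model needs defined visits.
2. For each of the six outcomes, specify a repeated-measures mixed model with arm, visit, arm-by-visit and the preoperative value, and an unstructured covariance. Include all randomised men with any postoperative value, and report the 12-month contrast.
3. Log-transform skewed outcomes such as residual urine and PSA, and state how zeros are handled. Say also how a missing preoperative value is handled: men enrolled with urinary retention may have no preoperative Qmax, and the covariate should not remove them.
4. Report loss by arm with reasons.
5. Add one sensitivity analysis that assumes worse values for the men lost, including those with no postoperative value.

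The cost is analysis wording only, with no extra patients, visits or measurements, and the named software can fit these models. The downside is the assumption that observed values explain the loss, which is why item 5 is needed. Kaplan-Meier proportions for delayed complications (outcome 8) are optional: they need onset dates, which the plan does not mention, and they assume that loss is unrelated to prognosis.

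### The sole primary outcome, catheter removal time, is a staff decision with no removal criterion, check times or masking stated, so a difference in removal decisions by energy source could enter the primary comparison

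*Combined protocol and SAP*

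**What the plan says.** Under Data collection and outcome measures, the single primary outcome is "Catheter removal time". Nothing there or elsewhere says when a catheter may come out, how often readiness is checked, or who decides. Masking of patients, ward staff or assessors is not mentioned.

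The assessments that are listed do not fill the gap:

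- The Postoperative Follow-up Protocol says "Patients will be evaluated immediately postoperative with vital signs (Blood pressure, Heart rate), abdominal examination, degree of haematuria, haemoglobin level drop", among other items. Haematuria is thus graded once, straight after surgery, and the grade is not linked to removal.
- The next visits are months later: "Patients will be re-evaluated at 6 and 12 months postoperatively with the IPSS". Secondary outcome 7 gives 1 and 12 months instead.

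Three other statements bear on the point:

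- Sample size rests on a previous study in which "mean catheter removal time in HoLEP group was 1.3 -/+0.6 while in Transurethral electrocautery enucleation group was 3.8 -/+1.7". No unit is given.
- Procedures states that "each procedure will be done by 2 expert surgeons who performed over 50 cases of enucleation with each energy source".
- The Introduction cites a study with earlier catheter removal after HoLEP. It also cites one with no statistical difference in safety and efficacy, and reports that enucleation relies on the surgeon's "skills rather than the energy source itself".

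Statistical Analysis compares the groups with a Student t-test and calls p below 0.05 significant.

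**The concern.** Time to catheter removal is not a spontaneous event. It ends when a member of staff judges that the catheter can come out. Randomisation balances the patients who enter the two arms, but it does not make later decisions about them the same.

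The surgeons necessarily know which energy source they used, and nothing in the plan keeps that from whoever decides on removal. The hospital is common to both arms and the surgeons appear to be, so a contrast between surgeons or sites is not the main worry. What remains is that the same clinician might, with similar urine and similar bleeding, remove sooner after one energy source than after the other.

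Such a gap would be indistinguishable from a treatment effect in the t-test. Analysts could not standardise it afterwards, because no record would show when each patient first met a common criterion. The plan tests against zero, so even a modest gap could be declared a significant difference.

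**Working it through.** **Inputs.** From Sample size: means 1.3 and 3.8, SDs 0.6 and 1.7, alpha 0.05, power 90%, 50 per group including 20% dropout, hence 50 × 0.8 = 40 evaluable. From Statistical Analysis: Student t-test, p<0.05. Assumed here: unit days, two-sided test.

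**The plan's own figure.** Planned difference = 3.8 − 1.3 = 2.5. Root-mean-square SD = sqrt((0.36 + 2.89)/2) = 1.275.

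- n per group = 2 × (1.960 + 1.282)² × 1.275² / 2.5² = 5.5, so 6, or 8 after dropout.
- With SD 1.7 in both arms, n = 9.7, so 10, or 13 after dropout.

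The stated 50 does not reproduce; it is larger than its inputs require. That is a separate matter. It is relevant here only because a trial of this size will find differences far below 2.5 significant.

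**Smallest observed difference reaching p<0.05.** SE = sqrt((SD₁² + SD₂²)/n); threshold = t(0.975, 2n − 2) × SE.

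| SDs | n per group | SE | Threshold (days) |
|---|---|---|---|
| 0.6 and 1.7 | 50 | 0.255 | 0.51 |
| 0.6 and 1.7 | 40 | 0.285 | 0.57 |
| 1.7 and 1.7 | 50 | 0.340 | 0.68 |
| 1.7 and 1.7 | 40 | 0.380 | 0.76 |

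These thresholds are about 20% (0.51/2.5) to 30% (0.76/2.5) of the planned difference.

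**Chance of p<0.05 with no true difference and an assumed average gap b in removal decisions.** Noncentral t with 2n − 2 degrees of freedom and noncentrality b/SE. For example, b = 0.5, n = 50 and the plan's SDs give 0.5/0.255 = 1.96.

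| SDs | n per group | b = 0.25 | b = 0.5 | b = 1.0 |
|---|---|---|---|---|
| 0.6 and 1.7 | 50 | 16.3% | 49.3% | 97.3% |
| 0.6 and 1.7 | 40 | 13.9% | 41.0% | 93.4% |
| 1.7 and 1.7 | 50 | 11.3% | 30.8% | 83.0% |
| 1.7 and 1.7 | 40 | 10.0% | 25.5% | 73.8% |

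With b = 0 the rate is 5%.

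**Set against the planned effect.** 0.5/2.5 = 20% and 1.0/2.5 = 40%. Gaps of this size could not by themselves produce an observed difference of 2.5.

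**Clock start.** A 2-hour shift between arms is 0.083 day. With the plan's SDs it moves the rejection rate from 5% to about 6%, which is negligible.

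**The case against.** The mechanism is inferred. The documents do not say who removes catheters, whether those people know the energy source, or whether the ward already has a common practice. One hospital and two surgeons experienced with both devices make a shared practice plausible. All of this stands, and it is why the point is limited to a possible gap of unknown size.

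A reader might go further and infer that the trial is biased towards HoLEP, because the planning figures favour it. The documents do not support that. The Introduction also credits skill over energy source and cites a comparison with no statistical difference, so what clinicians expect is not documented. Nor are the percentages above estimates of this trial's false-positive rate: b is assumed throughout.

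The illustration also supposes no true difference, far from the planned 2.5. That limits the point to smaller observed differences but does not remove it. The reference list describes the planning study as a retrospective comparison of monopolar with laser enucleation, whereas this trial uses bipolar, so a smaller true difference is quite possible.

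Pairing SDs of 0.6 and 1.7 with equal means is awkward, since those SDs come from groups with very different means. SD 1.7 in both arms is the more coherent case, and its lower rates should be read first. SD 0.6 in both arms would give higher rates, but is not relied on.

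Secondary outcomes such as haemoglobin drop, hospital stay, haematuria and retention can help show whether a catheter difference fits clinical recovery. They do not define removal.

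Finally, the unstated clock start and the choice between first and last removal after recatheterisation might be read as equally serious. They are not: the first has almost no effect, and for the second either choice is acceptable once written down.

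**Conclusion.** The point holds in limited form, and the plan should be changed. It is certain that the sole primary outcome has no removal criterion or check times and that masking is not mentioned. It is possible, not shown, that removal decisions differ by energy source; neither direction nor size can be derived from the documents.

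An observed difference near 2.5 would survive a gap of 0.5 to 1.0 day. A significant difference well below 2.5 would be hard to interpret, because a modest gap in decisions could produce it without any true difference. The illustrative rates rest on days as the unit, a two-sided test, 40 to 50 evaluable patients per group and an assumed gap. Confidence is medium, because the omission is clear but its consequence is not measurable in advance.

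**What to change.** Write one objective removal rule, identical in both arms. For example: remove the catheter at the first fixed check at which irrigation is off and haematuria is at or below a set grade. Specify the same check times after surgery for every patient. Existing ward staff make the checks and, where feasible, are not told the energy source. Allow departures for clinical need and record the reason.

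The study period begins in 4/2018, so enrolment may already have started. In that case apply the rule to the remaining patients, record the date of the change, and report the primary comparison also for patients treated before and after it.

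As wording only, state that time runs in hours from the end of surgery, and whether first or last removal is primary.

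The cost is protocol and case-report-form text, slightly less clinician discretion, and a few ward haematuria checks beyond the single immediate one now planned. No extra patients are needed. The rule reduces the possible bias but does not abolish it, since the operators cannot be masked.
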